### 16.6 Columbia-Suicide Severity Rating Scale (C-SSRS)

Suicidality will be monitored during the study using the C-SSRS. The C-SSRS is a questionnaire used to measure the presence and intensity of suicidal ideation and behavior. The C-SSRS will be completed at Screening, Days -7, -1, 1, 7, 14, and 28. The "Baseline/Screening" C-SSRS form will be completed at screening (lifetime history and past 24 months). The "Since Last Visit" C-SSRS form will be completed at subsequent time points.

Suicidal behavior and suicidal ideation will be summarized by visit for the Safety analysis set. The proportion of participants who meet the criterion for each of these categories at any post-baseline visit will be summarized as described in Table 8.

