6.2.2. Secondary Endpoint

• Change from baseline in vital signs, clinical laboratory analytes, electrocardiograms (ECGs), and responses on the Columbia–Suicide Severity Rating Scale (C-SSRS)

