- e. Other medications given at doses or in combinations that are likely to have a deleterious effect on cognitive performance, as described in the 2019 American Geriatrics Society Updated Beers® Criteria for Potentially Inappropriate Medication Use in Older Adults (American Geriatrics Society 2019)
- f. Prescribed cannabis or other THC-containing substances
- 10. Have an alcohol or drug use disorder within the past 12 months, as per DSM-5 criteria
- 11. Have a history of seizures or epilepsy, with the exception of a single episode of febrile seizures in childhood
- 12. Have current or recent suicidality, defined as follows:
 - a. Suicidal ideation within the past month, as evidenced by a score of 4 (active suicidal ideation with some intent to act, without specific plan) or 5 (active suicidal ideation with specific plan and intent) on the C-SSRS during Screening or Baseline
 - b. Suicidal behavior within the past year, as evidenced by a "Yes" on any of the 5 C-SSRS Suicidal Behavior Items (actual attempt, interrupted attempt, aborted attempt, preparatory acts, or behavior) on the C-SSRS during Screening or Baseline
 - c. Participant presents a serious risk of suicide in the opinion of the investigator
- 13. Have any of the following clinically significant medical conditions:
 - a. Any clinically significant finding on 12-lead ECG during Screening or Baseline
 - b. Supine vital signs outside of the following ranges during Screening or Baseline; vital sign measurements may be repeated once for initial values outside these ranges:
 - Heart rate <50 or >100 bpm
 - Systolic blood pressure <100 or >160 mmHg
 - Diastolic blood pressure <60 or >100 mmHg
- 14. Have a history, presence, and/or current evidence of serologic positive results for HIV-1 or HIV-2
- 15. Have a positive pregnancy test or be lactating at Screening or Day -1
- 16. Be investigative site personnel, sponsor personnel, or an immediate member of their family (spouse, parent, child, or sibling whether biological or legally adopted)

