12.1.8. Columbia–Suicide Severity Rating Scale

Suicidality will be monitored during the study using the C-SSRS (Posner 2011). This scale consists of a baseline evaluation that assesses the lifetime experience of the participant with suicidal ideation and behavior, and a postbaseline evaluation that focuses on suicidality since the last study visit. The C-SSRS includes 'yes' or 'no' responses for assessment of suicidal ideation and behavior as well as numeric ratings for severity of ideation, if present (from 1 to 5, with 5 being the most severe).

The "Baseline/Screening" C-SSRS form will be completed at Screening (lifetime history and past 24 months). The "Since Last Visit" C-SSRS form will be completed at all subsequent time points outlined in Table 2.

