# 9.2 Secondary Endpoints

- Change from baseline in vital signs, clinical laboratory analytes, and electrocardiograms (ECGs).
- Change from baseline for responses on the Columbia

  Suicide Severity Rating Scale (C-SSRS).

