#### Table 8 C-SSRS Categories for Analysis

Category	C-SSRS Item response is "YES"
Suicidal ideation	
 
Wish to be dead
 
Non-specific active suicidal thoughts
 
Active Suicidal Ideation with Any Methods
 
Active Suicidal Ideation with Some Intent
 
Active Suicidal Ideation with Specific Plan
 

Suicidal behavior	
 
Preparatory Acts or Behaviour
 
Aborted Attempt
 
Interrupted Attempt
 
Actual Attempt(non-fatal)
 
Completed suicide [1]
 

Suicidal Ideation or Behavior	Participant Engaged in Non-Suicidal Self-Injurious Behavior

 Completed suicide is not collected at the screening visit.

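### C-SSRS change from baseline is a secondary endpoint, but the SAP specifies no severity-level or baseline comparison, so worsening ideation need not appear in the tables

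*SAP*

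**What the plan says.** **Endpoint.** Protocol 6.2.2 defines the secondary endpoint as "Change from baseline in vital signs, clinical laboratory analytes, electrocardiograms (ECGs), and responses on the Columbia–Suicide Severity Rating Scale (C-SSRS"). SAP 9.2 lists the C-SSRS part separately, beginning "Change from baseline for responses on the Columbia", and SAP 16.0 repeats it among the safety measures.

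**What is collected.** Protocol 12.1.8 says the scale gives yes/no answers and "numeric ratings for severity of ideation, if present (from 1 to 5, with 5 being the most severe"). The form used at Screening covers lifetime history and the past 24 months. The since-last-visit form is used on Days -7, -1, 1, 7, 14 and 28 (SAP 16.6).

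**Who may enter.** Exclusion 12a in Protocol 8.2 concerns "Suicidal ideation within the past month, as evidenced by a score of 4" or 5. Levels 1 to 3 do not exclude on score. Exclusion 12c separately removes anyone the investigator considers a serious suicide risk.

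**What is summarised.** SAP 16.6 has two sentences on this. The first is "Suicidal behavior and suicidal ideation will be summarized by visit for the Safety analysis set". The second reads, in part, "proportion of participants who meet the criterion for each of these categories at any post-baseline visit will be summarized as described in Table 8". In that table there is a single ideation category. Five items stand against it, from a wish to be dead up to "Active Suicidal Ideation with Specific Plan". The SAP's table list contains one C-SSRS table, 14.3.6, and one C-SSRS listing, 16.2.12.

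**The concern.** The endpoint is a change, and the instrument grades ideation from 1 to 5. The specified summary uses neither the grade nor a baseline comparison. The other three components of the same secondary endpoint are treated differently. Laboratory values (SAP 16.2), vital signs (16.4) and ECGs (16.5) are all summarised as change from baseline. Vital signs and QTcF also have thresholds for the size of the change (Tables 6 and 7).

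At stake is whether the tables can show a participant who had mild ideation before dosing and moved on drug into the range that the protocol itself treats as disqualifying at entry. In a safety study of about 22 people, one such case matters. A secondary endpoint should not depend on someone finding it in a listing.

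**Working it through.** The plan has no C-SSRS figure to reproduce. The only calculated number is the approximately 22 participants to be dosed (20/0.90 = 22.2). It serves here only as a denominator.

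**Step 1: does any planned output measure change?** The any-post-baseline proportion counts everyone with a yes after dosing, whatever their baseline, so it compares nothing with baseline. The by-visit summary places baseline and later counts side by side, but at group level and without saying whether rows are items or categories. The general rule in Protocol 13.3 on change from baseline follows the description of continuous endpoints and does not say what change means for a yes/no item. So no within-participant change is defined.

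**Step 2: what does one ideation category lose?** Inputs: pre-dose level 0 to 3 (the levels exclusion 12a does not exclude on score) and highest post-dose level 0 to 5 (0 = none).

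- All pairs: 4 × 6 = 24.
- Upward moves: 5 from level 0, 4 from level 1, 3 from level 2, 2 from level 3; 5 + 4 + 3 + 2 = 14.
- Upward moves that start at level 1 or above, so that a yes/no flag stays at yes: 4 + 3 + 2 = 9.
- Moves into level 4 or 5: 4 × 2 = 8. Six of these start at levels 1 to 3 and leave the flag unchanged. The other two (0 to 4 and 0 to 5) turn it from no to yes, but do not show the level reached.

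**Step 3: illustration (hypothetical).** Of 22 dosed, one participant is at level 2 on the pre-dose record and level 4 on Day 7, and nobody else reports ideation. The ideation category reads 1/22 = 4.5% before and 1/22 = 4.5% on Day 7. A shift table would show one participant moving from 2 to 4.

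**Step 4: which record is baseline?** SAP 16.0 takes the last non-missing value before first dose. SAP Table 1 targets Day 1 pre-dose. If the Day 1 form is completed pre-dose, it normally covers about one day, back to Day -1. Two cases follow:

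- Low-level ideation is reported on that form: the flag is already yes, and Step 2 applies.
- Low-level ideation was reported only at Screening: the flag is no, and a later level 4 or 5 counts as new ideation.

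The unchanged-flag result therefore needs a positive pre-dose analysis record. An entry level of 1 to 3 at Screening is not enough.

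**The case against.** A reader might infer that the SAP expressly collapses the five levels into one flag. It does not. Table 8 lists the items separately under a column for a yes response, and the by-visit sentence names neither items nor categories. Table 14.3.6 could be programmed with item rows, and a level 4 or 5 response would then be visible as a count. One category remains the natural reading, because 16.6 speaks of categories and Table 8's category column has a single ideation entry. Item rows alone would still give no within-participant change.

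A reader might also infer that such a participant will register as unchanged on the endpoint, or would be hidden altogether. That goes too far, for three reasons:

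- The any-post-baseline proportion makes no baseline comparison for anyone, so the gap is an absent comparison, not a false finding of no change.
- Listing 16.2.12 shows the case by participant, and Protocol 13.6.7 requires type and/or category in the listings.
- Worsening of a pre-existing condition after the start of treatment is a TEAE (Protocol 12.2.1, SAP 16.1), so the event may reach the adverse event tables. This is not assured. SAP 16.2 and 16.4 say that clinically significant results will be captured as adverse events; 16.6 says nothing similar.

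Finally, 9 of 14 is not a rate. The documents do not say how many participants will have level 1 to 3 ideation before dosing, and exclusion 12c may reduce that number further. All of this limits the size of the point. None of it supplies the missing change summary.

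**Conclusion.** The point holds in a limited form. The plan names change from baseline in C-SSRS responses as a secondary endpoint and does not specify a summary that delivers it, although it does so for the other three components. On the natural reading of Table 8, worsening from level 1 to 3 to level 4 or 5 need not appear as a change in the planned tables. All 6 such moves leave a single flag at yes.

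This rests on two assumptions: that Table 14.3.6 follows the Table 8 categories without item rows, and that the participant's pre-dose analysis record is positive. If nobody reports level 1 to 3 ideation before dosing, the current plan loses only the level reached. The change is worth making because the data are already collected and the cost is small.

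**What to change.** In SAP 16.6 and Table 14.3.6:

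- Keep the Table 8 categories and show the five ideation items as separate rows.
- Add a shift table of pre-dose ideation level against highest post-dose level, each from 0 (none) to 5.
- Report the number and percentage of participants with any increase, and the number reaching level 4 or 5 after dosing.
- Define the pre-dose comparator as the highest level on the pre-dose since-last-visit forms (Days -7, -1 and pre-dose Day 1). State that for this table it replaces the last-value baseline of SAP 16.0.
- Show the lifetime and 24-month Screening history separately. If it entered the comparator, an old level 4 or 5 could mask a real increase on drug.

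The cost is some SAP wording and one small table from responses already collected. No procedure or visit changes. With about 22 participants, most cells will be zero.

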#### Table 8 C-SSRS Categories for Analysis

Category	C-SSRS Item response is "YES"
Suicidal ideation	
 
Wish to be dead
 
Non-specific active suicidal thoughts
 
Active Suicidal Ideation with Any Methods
 
Active Suicidal Ideation with Some Intent
 
Active Suicidal Ideation with Specific Plan
 

Suicidal behavior	
 
Preparatory Acts or Behaviour
 
Aborted Attempt
 
Interrupted Attempt
 
Actual Attempt(non-fatal)
 
Completed suicide [1]
 

Suicidal Ideation or Behavior	Participant Engaged in Non-Suicidal Self-Injurious Behavior

 Completed suicide is not collected at the screening visit.

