13.6.7. Columbia-Suicide Severity Rating Scale

Suicidality data collected on the C-SSRS at Baseline and by visit during the Treatment Period will be listed and summarized for all participants. Listings will include behavior type and/or category for Suicidal Ideation and Suicidal Behavior of the C-SSRS.

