Table 14.3.3.3.1	Urinalysis Results by Time Point Part 1 Continuous ∀ariables	Safety Analysis Set
Table 14.3.3.3.2	Urinalysis Results by Time Point Part 2 Categorical ∀ariables	Safety Analysis Set
Table 14.3.4.1	Vital Sign Results by Time Point	Safety Analysis Set
Table 14.3.4.2	Potentially Clinically Important Vital Sign Results	Safety Analysis Set
Table 14.3.5.1	Electrocardiogram Results	Safety Analysis Set
Table 14.3.5.2	Electrocardiogram Interpretations by Time Point	Safety Analysis Set
Table 14.3.5.3	Potentially Clinically Important Electrocardiogram Results	Safety Analysis Set
Table 14.3.6	Summary of Columbia–Suicide Severity Rating Scale (C-SSRS) Suicidal Ideation and Suicidal Behavior	Safety Analysis Set

Listing 16.1.7 Subject Enrollment  Listing 16.2.1.1 Discontinued Subjects from Study  Listing 16.2.1.2 Completion / Discontinuation of Investigational Product (IP)  Listing 16.2.2 Protocol Deviations  Listing 16.2.3.1 Subject Analysis Sets  Listing 16.2.4.1 Demographic and Baseline Data  All Screened Subjects  Safety Analysis Set  All Enrolled Subjects  Listing 16.2.3.1 Demographic and Baseline Data  Safety Analysis Set		 	1010C01110. 7 10-CNA-201
Listing 16.2.1.1 Discontinued Subjects from Study Safety Analysis Set  Listing 16.2.1.2 Completion / Discontinuation of Investigational Product (IP) Safety Analysis Set  Listing 16.2.2 Protocol Deviations Safety Analysis Set  Listing 16.2.3.1 Subject Analysis Sets All Enrolled Subjects			
Listing 16.2.1.1 Discontinued Subjects from Study Safety Analysis Set  Listing 16.2.1.2 Completion / Discontinuation of Investigational Product (IP) Safety Analysis Set  Listing 16.2.2 Protocol Deviations Safety Analysis Set  Listing 16.2.3.1 Subject Analysis Sets All Enrolled Subjects			
Listing 16.2.1.1 Discontinued Subjects from Study Safety Analysis Set  Listing 16.2.1.2 Completion / Discontinuation of Investigational Product (IP) Safety Analysis Set  Listing 16.2.2 Protocol Deviations Safety Analysis Set  Listing 16.2.3.1 Subject Analysis Sets All Enrolled Subjects			
Listing 16.2.1.1 Discontinued Subjects from Study Safety Analysis Set  Listing 16.2.1.2 Completion / Discontinuation of Investigational Product (IP) Safety Analysis Set  Listing 16.2.2 Protocol Deviations Safety Analysis Set  Listing 16.2.3.1 Subject Analysis Sets All Enrolled Subjects			

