Listing 16.2.5.2	Drug Accountability	Safety Analysis Set
Listing 16.2.5.3	Treatment Adherence	Safety Analysis Set

Listing 16.2.7.1	Adverse Events	Safety Analysis Set
Listing 16.2.7.2	Subjects with Adverse Events with Outcome of Death	Safety Analysis Set
Listing 16.2.8.1	Hematology and Coagulation Results and Change from Baseline	Safety Analysis Set

Listing 16.2.8.2	Biochemistry Results and Change from Baseline	Safety Analysis Set
Listing 16.2.8.3	Urinalysis Results and Change from Baseline	Safety Analysis Set
Listing 16.2.8.4	Pregnancy Test Results (Females of Childbearing Potential only)	Safety Analysis Set
Listing 16.8.5	Urine Drug Screen	Safety Analysis Set
Listing 16.2.9	Vital Signs	Safety Analysis Set
Listing 16.2.10.1	Electrocardiogram Results Part 1	Safety Analysis Set
Listing 16.2.10.2	Electrocardiogram Results Part 2	Safety Analysis Set
Listing 16.2.11.1	Physical Examinations	Safety Analysis Set
Listings 16.2.11.2	Neurological Examination	Safety Analysis Set
Listing 16.2.12	Columbia–Suicide Severity Rating Scale (C-SSRS)	Safety Analysis Set
Listing 16.2.13	Electroencephalogram (EEG) Monitoring Test	Safety Analysis Set
Listing 16.2.14	Magnetic Resonance Imaging (MRI) Test	Safety Analysis Set
Listing 16.2.15	Positron Emission Tomography (PET) Test	Safety Analysis Set
Listing 16.2.16	Alzheimer Disease History	Safety Analysis Set

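### As it reads, SAP Table 8 defines the combined ideation-or-behavior category by one non-suicidal self-injury item and by none of the ten suicidal items

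*SAP*

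**What the plan says.** C-SSRS responses are a secondary endpoint (protocol 6.2.2; SAP 9.2). SAP 16.6 plans two summaries. The first is by visit: "Suicidal behavior and suicidal ideation will be summarized by visit for the Safety analysis set". The second pools the post-baseline visits and refers to Table 8 for its categories: "The proportion of participants who meet the criterion for each of these categories at any post-baseline visit will be summarized".

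Table 8 has a category column and a column headed "C-SSRS Item response is" YES, so a participant falls in a category when a listed item is answered yes. It has three rows:

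- The ideation row lists five items, from a wish to be dead up to ideation with a specific plan.
- The behavior row lists five items, from preparatory acts up to completed suicide.
- The row labelled "Suicidal Ideation or Behavior" lists one item: "Participant Engaged in Non-Suicidal Self-Injurious Behavior".

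The table's only footnote says that completed suicide is not collected at screening.

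**The concern.** A category whose name joins ideation and behavior with 'or' should contain everyone who meets either. Here the label and the criterion disagree twice. The row contains none of the items that would make a participant suicidal under the two rows above, and the one item it does contain is described as non-suicidal.

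The combined row is the figure a reader would take as the share of participants with any suicidality. If it is programmed from Table 8 as it reads, that share could be too low, too high, or right in total while counting the wrong people.

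**Working it through.** The plan states no figure for this category and no expected C-SSRS event rate, so there is nothing to reproduce. The check compares the item lists and then works through the smallest cases.

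**Inputs**

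- Items per row (SAP Table 8): ideation 5, behavior 5, combined row 1.
- Planned number dosed: up to 22, to obtain up to 20 completers (protocol 7.2). The Safety Set is everyone dosed (SAP 11.1), so n = 22 is the natural denominator; n = 20 is shown for comparison.

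**Step 1: overlap of items**

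- A union of the first two rows would hold 5 + 5 = 10 items.
- The combined row as written shares 0 of those 10 and holds 1 item found in neither.

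**Step 2: how single participants are classified**

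| Participant has | Ideation row | Behavior row | Combined row as written | Combined row as a union |
|---|---|---|---|---|
| Ideation only | yes | no | no | yes |
| Attempt only | no | yes | no | yes |
| Non-suicidal self-injury only | no | no | yes | no |

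All three are classified wrongly in the combined row as written.

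**Step 3: size of the error**

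Let k be the number of participants with ideation or behavior and no self-injury, and m the number with self-injury only. Participants with both are counted either way, so

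error in the combined row = (m − k)/n.

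One participant moves the row by 1/22 = 4.5 points (1/20 = 5.0 points).

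Illustrative cases at n = 22:

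| k | m | Combined row as written | True union | Error |
|---|---|---|---|---|
| 1 | 0 | 0/22 = 0% | 1/22 = 4.5% | −4.5 points |
| 0 | 1 | 1/22 = 4.5% | 0/22 = 0% | +4.5 points |
| 1 | 1 | 1/22 = 4.5% | 1/22 = 4.5% | 0, with two participants misclassified |

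If the one case in the first line is ideation, the combined row reads 0% beside an ideation row of 4.5%, which no true union can do. In the third line the totals agree, so a comparison with the ideation row would not reveal the error.

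**Step 4: does another section supply the union?**

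- The running text of SAP 16.6 names only ideation and behavior.
- Protocol 13.6.7 does the same: "Listings will include behavior type and/or category for Suicidal Ideation and Suicidal Behavior of the C-SSRS".
- The title of planned Table 14.3.6 in SAP Appendix F ends "Rating Scale (C-SSRS) Suicidal Ideation and Suicidal Behavior".
- Protocol 12.1.8 describes the scale without a composite. The behavior items listed in protocol 8.2 (exclusion criterion 12b) do not include non-suicidal self-injury.

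None of these defines a combined category, and none supports treating self-injury without suicidal intent as suicidal.

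**The case against.** **The table may be damaged.** Neighboring SAP tables clearly suffered in the PDF reading: the headers of Table 7 are cut short, and Table 5 has a row with no parameter name. In Table 8 the first two rows carry list formatting and the third does not. Two original rows, a composite and a separate self-injury row, could have run together there. This is possible but unproven: a one-item cell may simply not have been set as a list, and the row shows no gap or redaction mark. The objection stands as a reason to check the original first.

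A reader might infer that the defect survives even a lost row boundary, because the combined category would then have no items at all. The documents do not support that. Content could have been lost with the boundary. Also, a row with that name directly beneath itemized ideation and behavior rows would be understood as their union, leaving only a missing explicit definition.

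**The row may never be produced.** A reader might also infer that Table 14.3.6 is bound to show a wrong combined figure. In SAP 16.6 the phrase about these categories follows a sentence naming only behavior and ideation, and the title of Table 14.3.6 names only those two. Against this, the summary is to follow Table 8, whose title calls its rows the categories for analysis. Tabulation is likely but not certain.

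**A programmer would know what was meant.** Perhaps, but there are two candidate corrections: a union of the ten items, or a relabelled self-injury row. They give different numbers.

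**The numbers are only 1/n.** Correct. They show what one participant does to the row, not how often an error would occur.

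**Conclusion.** As it reads, the Table 8 criterion for the combined category is wrong for its label: it holds 0 of the 10 suicidal items and 1 item that is not suicidal. Followed literally, it misclassifies each participant with ideation or behavior but no self-injury, and each with self-injury only. Each one moves the row by 4.5 points at n = 22.

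The point is minor. The separate ideation and behavior rows are correctly itemized. Listing 16.2.12 covers the "Suicide Severity Rating Scale (C-SSRS") data by participant, and with about 22 participants it can be read directly. The primary endpoint is untouched, and no decision rule in either document uses the combined row. Nothing supports a claim that the study's conclusions on suicidality would be wrong.

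The conclusion rests on two assumptions: that the original table reads as the extracted text does, and that the combined row is tabulated. If the first fails because two rows merged, what remains is an unstated but obvious union. If the original gives the combined category its own items, the point falls.

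**What to change.** 1. Check Table 8 in the original SAP for a lost row boundary or lost cell content.
2. If it reads as above, define the combined category as a yes to any of the five ideation or five behavior items in Table 8, at any post-baseline visit.
3. Report non-suicidal self-injurious behavior in a row of its own, outside the suicidal categories.
4. State in SAP 16.6 whether Table 14.3.6 shows the combined category.

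The cost is one row reworded, one row added and one clarifying sentence, with no new data, assessments or analyses. If the database is already locked, SAP 6.0 requires the change and its justification to be described in the clinical study report.
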